7. MONITORING OF ADVERSE EVENTS AND MANAGEMENT

7.1. Monitoring and Reporting of Adverse Events

7.1.1. Definitions

An adverse event is defined as "any untoward medical occurrence in a patient or clinical investigation subject administered a pharmaceutical product that does not necessarily have a causal relationship with this treatment" (ICH Guidelines E2A). An adverse event can further be broadly defined as any untoward deviation from baseline health, which includes:

- Worsening of conditions present at the onset of the study
- Deterioration due to the primary disease
- Concurrent illness
- Events related or possibly related to concomitant medications

(International Centers for Tropical Disease Research Network Investigator Manual, Monitoring and Reporting Adverse Events, 2003).

7.1.2. Identification of Adverse Events

At each scheduled and unscheduled visit to the clinic, study clinicians will assess in all pregnant women who have started study drugs, according to a standardized case record form. A severity grading scale, based on toxicity grading scales developed by the NIH Divisions of AIDS (DAIDS) and the Division of Microbiology and Infectious Diseases (DMID) Toxicity Tables, will be used to grade severity of all symptoms, physical exam findings, and laboratory results (Appendix I). All pregnant women, regardless of treatment arm, will be assessed using the same standardized case record form. Adverse event monitoring will occur during the period when study drugs are given and up to 6 weeks post-partum.

Data will be captured on the incidence of all adverse events, regardless of severity. For each adverse event identified and graded as severe or life threatening and felt to be possibly, probably or definitely related to study drugs, an adverse event report form will be completed. In addition, an adverse event form will be completed for all serious adverse events and unexpected events, regardless of severity. An adverse event report form will not be completed for events classified as mild or moderate (unless they are serious or unexpected), as mild and moderate symptoms are common and difficult to distinguish from signs and symptoms due to malaria and other common illnesses. The following information will be recorded for all adverse experiences that are reported:

- 1) Description of event
- 2) Date of event onset
- 3) Date event reported
- 4) Maximum severity of the event
- 5) Maximum suspected relationship of the event to study drugs (either SP or DP)
- 6) Whether the event is a serious adverse event
- 7) Initials of the person reporting the event
- 8) Outcome
- 9) Date event resolved

7.1.3. Reporting of Adverse Events

Guidelines for reporting of adverse events provided by NICHD, UCSF Committee for Human Research (CHR), and the Food and Drug Administration (FDA) in the U.S. and the Makerere

University IRB (SBSREC), and National Drug Authority (NDA) in Uganda will be followed as summarized in Table 2 below.

Institution	Type of Adverse Events	When to Report
UCSF-CHR	 External (off-site) Adverse Events are: AEs that occur in study participants who are not enrolled at a UCSF or affiliated study site. These AEs occur at sites that are under the oversight of another IRB. 	• Not applicable
MU-SBSREC	All Serious and Unexpected events irrespective of relationship	 Fatal or life-threatening events within 3 working days of awareness All other SAEs within 7 calendar days
NDA	All Serious and Unexpected events irrespective of relationship	• Within 7 calendar days of awareness
FDA	 Definitely, Probably or Possibly related AND BOTH Serious[*] AND Unexpected[±] 	 For fatal or life-threatening events, by telephone or fax within 7 calendar days of first awareness All other reportable events within 15 calendar days of first awareness

Table 2. Guidelines for reporting adverse events

Serious Adverse Event (SAE) is any AE that results in any of the following outcomes:

- Death,
- Life-threatening adverse experience.
- Inpatient hospitalization or prolongation of existing hospitalization,
- Persistent or significant disability/incapacity,
- Congenital anomaly/birth defect, or cancer, or

• Any other experience that suggests a significant hazard, contraindication, side effect or precaution that may require medical or surgical intervention to prevent one of the outcomes listed above,

• Event that changes the risk/benefit ratio of the study.

Unexpected Adverse Event An adverse event is defined as being unexpected if the event exceeds the nature, severity, or frequency described in the protocol, consent form and investigator brochure (when applicable). An unexpected AE also includes any AE that meets any of the following criteria:

- Results in subject withdrawal from study participation,
- Due to an overdose of study medication, or
- Due to a deviation from the study protocol

8. STATISTICAL CONSIDERATIONS

8.1. Hypothesis 1

We will test the hypothesis that pregnant women who receive IPTp with monthly DP will have a lower risk of a composite adverse birth outcome defined as LBW, preterm delivery or SGA compared to those who receive monthly SP. Secondary outcomes will include incidence of malaria and adverse events during pregnancy, risk of asymptomatic parasitemia and anemia during pregnancy, and measures of placental malaria at the time of delivery. For women with non-singleton birth (i.e. twins), dichotomous delivery outcomes at the level of the individual child/placenta will be based on whether the outcome was present in either child/placenta.

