6.9. Duration of Follow-up and Criteria for Premature Study Withdrawal

Pregnant women will be followed until their 6 week postpartum visit. Children will be followed until they reach 12 months of age. Study participants will be prematurely withdrawn from the study for: 1) movement out of study area, 2) inability to be located for > 60 consecutive days, 3) withdrawal of informed consent, 4) inability to comply with the study schedule and procedures, 5) at the discretion of the site investigator if the study is not in the best interest of the participant, 6) subject or parent/guardian judged by the site investigator to be at significant risk of failing to comply with the study protocol as to cause them harm or seriously interfere with the validity of study results, 7) women found to have become HIV infected at the time of delivery (child withdrawal only). If a subject is withdrawn for reasons # 1-3, we will be unable to perform any additional study procedures. If a subject is withdrawn for reasons # 4-6, plans to obtain appropriate follow-up tests outside of the study will be individualized for each subject depending on the health status of the subject at the time of withdrawal and the willingness of the participant and his or her parent/guardian to proceed with additional testing. If a subject is withdrawn for #7, they will be referred for appropriate care following local PMTCT guidelines.

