6.12. Management of Adverse Events Potentially Related to Study Drugs

The following section outlines management of adverse events potentially related to study drugs (SP or DP) among pregnant women. Given the double blinded nature of the intervention, study clinicians and study participants will not be aware of what study drugs are being administered. Therefore all women will be considered potentially exposed to either study drug during the period study drugs are first given up to the completion of follow-up (6 weeks post-partum).

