8.1.2. Secondary Outcomes

Secondary outcomes are summarized in Table 3 below.

Secondary outcome	Definition
Placental malaria by histopathology	Any evidence of placental infection (parasites or
	pigment)
Placental parasitemia	Proportion of placental blood samples positive for
	parasites by microscopy or LAMP
Maternal malaria	Any treatment for malaria during pregnancy
Incidence of adverse events	Adverse events stratified by type, severity score
	and relationship to study drugs
Prevalence of anemia	Proportion of routine hemoglobin measurements
	< 11 g/dL & < 8 g/dL
Prevalence of asymptomatic	Proportion of routine monthly samples positive
parasitemia	for parasites by microscopy and LAMP

Table 3. Secondary outcomes

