8.1.3. Analyses

A modified intention-to-treat approach to all analyses will be used, including all study participants randomized to therapy and have the outcome of interest measured including all

follow-up time until the study participants complete the study or early study termination regardless of whether the intervention was stopped due to an adverse event.

Primary analysis. We will compare the risk of having any adverse birth outcome between the study arms using the Chi-Square or Fisher's exact test. We will explore for any differences of potential confounders between the treatment arms and if necessary adjust our analysis using multivariate logistic regression. We will also perform sub-group analyses comparing the risks of having individual adverse birth outcome (LBW, preterm delivery, SGA) between the study arms using the Chi-Square or Fisher's exact test.

Secondary analyses. We will compare the prevalence of different definitions of placental malaria (placental parasitemia by microscopy, placental malaria by LAMP, placental malaria by histopathology) using the Chi-Square or Fisher's exact test. We will compare the incidence of maternal malaria and adverse events using Poisson or negative binomial regression models. The Poisson models will include the logarithm of the follow-up time as an offset. We will translate the fitted coefficients and their confidence bounds into percentage effects with the formula 100*[exp(coefficient)-1]. This approach is closely related to exponential survival models for analyzing events per follow-up time, but is better able to adjust for violated assumptions. Testing for overdispersion in the Poisson regression can detect violations of these assumptions, and variances can be adjusted accordingly to produce valid p-values and confidence interval. If significant deviations from required distributions in study data are detected, we will employ negative-binomial or zero-inflated negative-binomial models to account for the observed pattern of data. We will compare the prevalence of maternal anemia and asymptomatic parasitemia using generalized estimating equations with adjustments for repeated measures in the same study participant. If necessary, multivariate analyses will be performed to adjust for potential confounders and effect modifiers.

8.2. Hypothesis 2

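### The adverse-event outcome is named as events during pregnancy, but the analysis runs over follow-up to 6 weeks postpartum; one window should govern both the event count and the offset

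*Combined protocol and SAP*

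**What the plan says.** Objective 1 (2.1) and the opening of 8.1 share one sentence: "Secondary outcomes will include incidence of malaria and adverse events during pregnancy". The time qualifier covers malaria and adverse events alike.

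Section 8.1.3 sets one person-time rule for all analyses, regardless of whether the intervention was stopped: women contribute "follow-up time until the study participants complete the study or early study termination". It names no date. Section 6.9 supplies it: "Pregnant women will be followed until their 6 week postpartum visit". Maternal malaria and adverse events are both analysed as rates: "The Poisson models will include the logarithm of the follow-up time as an offset".

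Table 3 treats the two outcomes differently. Maternal malaria is limited in time: "Any treatment for malaria during pregnancy". The adverse-event row has no limit: "Adverse events stratified by type, severity score", followed by relationship to study drug. The interim safety statistic in 8.5.2, a rate ratio for grade 3/4 events and SAEs, has no stated window either.

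On collection, 7.1.2 says: "Adverse event monitoring will occur during the period when study drugs are given and up to 6 weeks post-partum". Section 6.12 regards every woman as potentially exposed to either drug over the same span.

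**The concern.** In a rate model the window fixes two things at once, the events counted and the person-time in the offset. Here the named outcome supplies one window and the analysis rule supplies another. An analyst who followed both literally would divide pregnancy-only events by person-time that includes the six weeks after delivery. An analyst who harmonised them could go either way, and nothing in the plan stops that choice from being made once the data have been seen.

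Maternal safety is one of the evidence gaps the trial was set up to fill (1.1 and 1.3), and doses are scheduled as late as week 40 (Appendix D). Whether the weeks after delivery count should therefore be settled in advance.

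**Working it through.** **1. The plan's own figure.** The only stated sample size is for the birth outcome. With 30.4% v 21.4%, two-sided alpha 0.05, 80% power and no continuity correction, the requirement is 371 per arm. Then 371/0.95 = 390.5, rounded up to 391, and 2 x 391 = 782. This matches 8.4. The adverse-event window does not enter it.

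**2. The two windows side by side.**

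| Source | End of adverse-event window |
|---|---|
| 2.1, 8.1 (outcome as named) | End of pregnancy |
| 8.1.3 with 6.9 (analysis person-time) | 6-week postpartum visit |
| 6.12, 7.1.2 (exposure, collection) | 6 weeks postpartum |
| Table 3, 8.5.2 | Not stated |

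**3. Postpartum share from the schedule.** Share = 6 / (weeks from start to delivery + 6). Delivery week is an assumption, 37 to 40.

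- First dose at week 16, delivery at 40: 6/30 = 20.0%.
- First dose at week 20, delivery at 40: 6/26 = 23.1%.
- First dose at week 20, delivery at 37: 6/23 = 26.1%.
- Counting from enrolment at week 12, delivery at 40: 6/34 = 17.6%.

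The range is 18-26%.

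**4. Check against the earlier Tororo trial.** Adverse-event person-years are recovered from Table 9 as events/rate (abdominal pain row). Person-years at risk during pregnancy are printed in 1.2.

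| Arm (women) | Table 9 | Pregnancy | Postpartum share | Extra weeks per woman |
|---|---|---|---|---|
| 3 dose SP (106) | 172/3.14 = 54.8 | 43.0 | 21.5% | 5.8 |
| 3 dose DP (94) | 122/2.52 = 48.4 | 38.2 | 21.1% | 5.7 |
| Monthly DP (100) | 132/2.47 = 53.4 | 42.3 | 20.8% | 5.8 |
| Pooled | 156.6 | 123.5 | 21.2% | |

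The surplus of nearly six weeks per woman suggests that Table 9 ran to 6 weeks postpartum. This is an inference, because the protocol does not print that table's window.

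**5. Effect of mixing the windows.** Pregnancy-only events over full person-time give 123.5/156.6 = 0.79 of the true pregnancy rate, about 21% too low. This applies about equally in both arms, so the rate ratio is largely preserved while the rates are wrong.

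**6. Precision under a consistent pregnancy-only window.** Take 391 women per arm, person-time per woman as in the monthly DP arm, and Table 9 grade 3-4 rates of 0.33 (3 dose SP) and 0.17 (monthly DP) per person-year. SE of the log rate ratio = sqrt(1/e1 + 1/e2).

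- Full window: 53.4/100 x 391 = 208.8 person-years per arm; events 68.9 + 35.5 = about 104; SE 0.207.
- Pregnancy only, constant rate: 42.3/100 x 391 = 165.4 person-years per arm; events 54.6 + 28.1 = about 83; SE 0.232, or 12% larger.
- Pregnancy only, all events by delivery: the count stays near 104 and the SE near 0.207, a loss of about 0%.

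The constant rate is doubtful. Of the 18 + 9 = 27 grade 3-4 events in those two Table 9 arms, 18 were anemia and 2 thrombocytopenia, so 20 of 27 were laboratory findings. Appendix G schedules CBC and ALT at enrolment, weeks 20, 28 and 36, and delivery, with none at 1 or 6 weeks postpartum.

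**The case against.** The best reply is that the plan already points one way. Sections 2.1 and 8.1 are summary sentences. Table 3 holds the definitions: it confines malaria to pregnancy and leaves adverse events unconfined. Section 8.1.3 then takes all follow-up, and 6.12 and 7.1.2 use the same span. The earlier trial seems to have done likewise. This stands as a reading of intent. It does not remove the conflict, because the outcome as named in the objective and in the statistical section still says otherwise and no sentence says which governs.

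Several stronger readings are tempting and are not supported:

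- A reader might infer that 7.1.2 itself contradicts 8.1. It sets a collection window, and collecting for longer than one analyses is not an inconsistency. The analytical conflict is between 2.1/8.1 and 8.1.3, and even 8.1.3 reaches 6 weeks postpartum only through 6.9.
- A reader might infer that postpartum deaths or SAEs would go unseen. Section 7.1.3 sends serious events to the ethics committee and the national drug authority irrespective of relationship, and 8.5.3 gives the DSMB cumulative SAEs by arm. At most they drop out of the planned rate comparison.
- A reader might take 12% as the expected loss of precision. It needs a constant event rate, which the laboratory schedule makes unlikely.
- A reader might infer that a pregnancy-only window discards all follow-up after the last doses. The time from the week 36 dose to delivery remains in it. The piperaquine half-life argument also cuts both ways: 1.3 stresses its length, while 1.1 cites a study finding a shorter terminal half-life in pregnancy.
- A reader might infer a biased comparison. Both arms are treated alike, and the ratio shifts only if the postpartum ratio differs from that in pregnancy. The documents give no evidence on this.

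**Conclusion.** The point holds as a modest inconsistency in a secondary safety outcome. The longer window is the better-supported reading, but 2.1 and 8.1 contradict it, and combining the two rules literally gives rates about one fifth too low.

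The size rests on stated assumptions. The share is about 21% if the earlier trial's person-time carries over, and 18-26% across the assumed start and delivery weeks. The precision range of about 0-12% runs from all grade 3-4 events falling by delivery to an equal rate before and after it. A larger loss would need a higher rate after delivery than before, for which the documents give no figures. The calculation also assumes Poisson variation. The primary outcome and N = 782 are untouched.

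**What to change.** - In 2.1, 8.1 and Table 3, state the adverse-event window as first study-drug dose to 6 weeks postpartum, matching 6.12 and 7.1.2.
- In 8.1.3, say that the adverse-event count and its offset both use that window. Apply the same window to the rate ratio in 8.5.2.
- Keep maternal malaria restricted to pregnancy and give it a pregnancy-only offset. The general rule in 8.1.3 otherwise creates the same mismatch there.
- Report adverse events before and after delivery separately, and say on which side events on the day of delivery fall.

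The cost is wording in five places plus one extra tabulation; the data are already collected. There are two downsides. Delivery-related events unrelated to drug enter the count, and laboratory event rates are diluted because no CBC or ALT is scheduled after delivery. The before/after split makes both visible. The change should be made before unblinded outcome data are examined.

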8.1.1. Primary Outcome

The primary outcome will be the risk of having an adverse birth outcome defined as the occurrence of any of the following:

- 4) Low birth weight (< 2500 gm)
- 5) Preterm delivery (< 37 weeks gestational age)
- 6) Small for gestational age (< 10th percentile relative to an external growth reference)⁷³

8.1.2. Secondary Outcomes

Secondary outcomes are summarized in Table 3 below.

Secondary outcome	Definition
Placental malaria by histopathology	Any evidence of placental infection (parasites or
	pigment)
Placental parasitemia	Proportion of placental blood samples positive for
	parasites by microscopy or LAMP
Maternal malaria	Any treatment for malaria during pregnancy
Incidence of adverse events	Adverse events stratified by type, severity score
	and relationship to study drugs
Prevalence of anemia	Proportion of routine hemoglobin measurements
	< 11 g/dL & < 8 g/dL
Prevalence of asymptomatic	Proportion of routine monthly samples positive
parasitemia	for parasites by microscopy and LAMP

Table 3. Secondary outcomes

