5.2. Treatment Allocation

On the day of enrollment, pregnant women will be referred to a study pharmacist responsible for treatment allocation. The study pharmacist will assign treatment arms as follows:

- 1. Select next available envelope
- 2. Note treatment number on the outside of the envelope
- 3. Write date, time, and study number on the outside of the envelope
- 4. Open envelope
- 5. Remove form containing code for treatment arm and date, time, and study number (transferred to form via carbon paper inside of envelope)
- 6. Store form in lockable file box in study pharmacy
- Record onto the treatment allocation master list the study number, enrollment date, treatment assignment code, treatment arm, and study medications to be given during pregnancy
- 8. Store treatment allocation Master list in a lockable cabinet in study pharmacy
- 9. Record treatment number in the study participant's file

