CareStart Pf HRP-2 (Access Bio Inc USA) RDT testing using the PTS reader will be performed at enrollment and every 4 weeks at the time of routine visits during pregnancy. Approximately 5 μ L of whole blood will be placed on the cartridge, which is inserted into the reader, and the reader will take approximately 1-3 minutes to complete the testing. The graphical user interface (GUI) guides the user through the assay process. Quantitative PCR will be performed at enrollment and at the time of routine visits using standardized procedures on \sim 100ul of whole blood. A HRP2-based experimental RDT will be tested at enrollment and every 8 weeks at the time of routine phlebotomy during pregnancy using \sim 100ul of whole blood. An RDT result will be considered positive if both the control line and the test line are visible after the development time. A result will be considered negative if the control line is visible, but no test line appears. The result will be considered invalid if no control line is visible, regardless of whether or not a test line appears. A hemozoin-based experimental rapid diagnostic test (MOD) will be performed at routine visits in a subset of children using ~ 50ul of whole blood collected by finger prick or phlebotomy. Approximately 50ul of whole blood will be placed in a special cuvette with a custom dilute, which is inserted into the sonicator and then the reader, and it will take approximately 2 minutes to complete the testing. For samples undergoing parasite detection by magnetic levitation, less than 10 µL of blood will be mixed with a paramagnetic

agent such as gadolinium, placed in close proximity to the earth magnets, and visualized by microscopy and/or a magnified imaging system.

Procedures for reporting and follow up of incidental concerning metabolite testing results Participants will be considered at elevated risk for Sickle Cell Disease (SCD) or Congenital Hypothyroidism (CH) according to the following criteria:

 SCD: Patterns of adult hemoglobins [HbA(A) and variants (S,C,D,E, B-thal)] as well as hemoglobin peak percentages (HGB-FAST, HGB-F1, HGB-F, HGB-F+F1, HGBFAST+ F1, HGB-Other, HGB-A] based on the interpretation of the lowa testing laboratory.

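### Table 3 and section 8.1.3 give no start for maternal malaria, parasitaemia and anaemia, so data from before the first study-drug dose can enter and dilute these secondary estimates

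*Combined protocol and SAP*

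**What the plan says.** Table 3 in section 8.1.2 defines three maternal secondary outcomes without a start:

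- maternal malaria: "Any treatment for malaria during pregnancy";
- asymptomatic parasitaemia: "Proportion of routine monthly samples positive" for parasites;
- anaemia: "Proportion of routine hemoglobin measurements" below 11 and below 8 g/dL.

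Section 8.1.3 includes all "follow-up time until the study participants complete the study or early study termination". That fixes the end of follow-up. It gives no origin for the follow-up or for the log follow-up time used as the offset.

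Randomisation precedes dosing. Women enter at 12-20 weeks (section 4.1), and section 5.2 says: "On the day of enrollment, pregnant women will be referred to a study pharmacist responsible for treatment allocation". Study drug is given every 4 weeks from week 16 to week 40 (section 5.4, Appendix D). The Appendix G footnote limits the week-16 visit to women enrolled before 16 weeks, so the others start at week 20. Under section 6.5 study drug is given at the routine visit, where blood is also drawn.

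Elsewhere the plan does state a start. Infant time at risk begins at birth (section 8.2.1). For adverse events, also a Table 3 outcome, section 7.1.2 says "study clinicians will assess in all pregnant women who have started study drugs", and adds: "Adverse event monitoring will occur during the period when study drugs are given and up to 6 weeks post-partum".

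**The concern.** Up to about 4 weeks can pass between randomisation and first dose. Read literally, Table 3 counts malaria treated in that gap, and it counts the routine monthly sample taken at the first-dose visit. The assigned drug cannot have influenced either. Data of this kind have the same expected value in both arms, so they shrink the estimated difference.

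Whether the enrolment haemoglobin counts is unclear. Section 4.4 calls the enrolment tests baseline, while section 6.10.2 places the enrolment sample among the routine clinical laboratory studies.

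At stake is the size of effect reported for the maternal malaria outcomes in Objective 1. Two analysts could also follow the plan faithfully and report different estimates from the same data.

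**Working it through.** The plan states no size or power for these outcomes, so there is no planned figure to reproduce. The evaluable number per arm follows from section 8.4: 391 × 0.95 = 371.

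**Parasitaemia.** Appendices D and G give 7 routine samples (weeks 16-40) if enrolled before 16 weeks, and 6 (weeks 20-40) otherwise. The first is pre-dose, so the pre-dose share f is 1/7 or 1/6. The enrolment sample is left out here. Assume that the earlier trial's 40.5% (3-dose SP) and 5.2% (monthly DP), from section 1.2, are post-dose values. Pre-dose prevalence is not given; assume 30-60%.

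Observed prevalence = (1 − f) × post-dose + f × pre-dose.

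- No pre-dose samples: 5.2/40.5 = 0.13; difference 35.3 points.
- f = 1/7, pre-dose 30%: 8.74/39.0 = 0.22.
- f = 1/7, pre-dose 40.5%: 10.24/40.5 = 0.25.
- f = 1/6, pre-dose 40.5%: 11.08/40.5 = 0.27.
- f = 1/6, pre-dose 60%: 14.33/43.75 = 0.33.
- Difference: 35.3 × 6/7 = 30.3 points; 35.3 × 5/6 = 29.4 points.

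**Maternal malaria.** Assume uniform enrolment over 12-20 weeks (mean gap to first dose 2.0 weeks), delivery at 39.5 weeks (mean follow-up 23.5 weeks), and a pre-dose rate equal to the earlier SP rate of 41/43.0 = 0.953 per person-year. Then f = 2.0/23.5 = 0.085, and the observed rate ratio is f + (1 − f) × true ratio.

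Pre-dose episodes per arm: 371 × (2/52.18) × 0.953 = 13.6. Post-dose DP episodes: 371 × (21.5/52.18) × 0.953 × true ratio = 145.7 × true ratio.

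| True rate ratio | Reads as | Post-dose DP episodes | Pre-dose share of DP episodes |
|---|---|---|---|
| 0.05 | 0.13 | 7.3 | 65% |
| 0.25 | 0.31 | 36.4 | 27% |
| 0.50 | 0.54 | 72.8 | 16% |

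Halving the pre-dose rate lowers the 65% to 6.8/(6.8 + 7.3) = 48%.

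**Anaemia.** Appendix G schedules blood counts at enrolment and weeks 20, 28 and 36, with no week-20 draw if enrolled at 18-20 weeks. Pre-dose values over antenatal values are:

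| Enrolled at (weeks) | Weight (uniform enrolment) | Enrolment value as baseline | Enrolment value counted |
|---|---|---|---|
| under 16 | 0.50 | 0/3 | 1/4 |
| 16-18 | 0.25 | 1/3 | 2/4 |
| 18-20 | 0.25 | 0/2 | 1/3 |

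Pooled: 0.25/2.75 = 9% with the enrolment value as baseline, and 1.25/3.75 = 33% with it counted. Adding the delivery haemoglobin gives 0.25/3.75 = 7% and 1.25/4.75 = 26%. The prevalence difference shrinks by the same share.

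**The case against.** The strongest reply is that counting from randomisation is the intention-to-treat default. Section 8.1.3 covers everyone randomised and all their follow-up. The effect of assignment from that point is a valid estimand, and preferring post-dose time is a choice. That stands. The plan's approach is legitimate and biases neither arm; it answers a more diluted question.

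Second, the plan is silent rather than explicit. A reader might infer that it expressly counts pre-dose malaria and pre-dose person-time. No sentence says so. Section 8.1.3 treats maternal malaria and adverse events together, and the only maternal origin stated anywhere is study-drug start (section 7.1.2), so a drug-start reading is available. A reader might also infer that the enrolment parasite sample counts. Section 6.10.4 points the other way: "Quantitative PCR will be performed at enrollment and at the time of routine visits using standardized procedures" lists enrolment apart from routine visits. The first-dose-visit sample has no such escape, because it is taken at a routine visit. Treatment before enrolment cannot enter, since section 4.2 excludes those women.

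Third, the size depends on borrowed figures. It is tempting to say that most malaria episodes in the DP arm would be pre-dose. The documents do not support that as a general statement: the share is 65% at a true ratio of 0.05 but 51% at 0.09, 27% at 0.25 and 16% at 0.50. The earlier monthly DP arm had 0 episodes in 42.3 person-years. With 8.5% of that time pre-dose at 0.953 per person-year, about 3.4 would be expected (42.3 × 0.085 × 0.953). That trial may therefore have counted from first dose, or the pre-dose rate may be lower than assumed here. Nor do the documents show that 40.5% and 5.2% are post-dose values; section 1.2 says only that they were measured during pregnancy. If they already include pre-dose samples, the parasitaemia calculation dilutes twice.

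**Conclusion.** The point holds as an unstated origin for three secondary outcomes. The literal wording lets pre-dose data in and attenuates the estimates. It is neither an error in the comparison nor a bias towards one arm.

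Under the assumptions above, the parasitaemia ratio moves from 0.13 to about 0.22-0.33, and the difference from 35 to 29-30 points. Dilution of the malaria rate ratio is modest in absolute terms, and lower still if the pre-dose rate is below the SP rate. For anaemia the size turns on how the enrolment haemoglobin is classified. The enrolment distribution, pre-dose rates and on-drug effects are assumptions, and the earlier SP arm received 3 doses, not monthly dosing.

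A reader might infer that the parasitaemia or malaria findings would be lost. Effects as large as the earlier trial's would probably still be detected, only understated. Any loss of power for anaemia cannot be worked out from the documents. Type I error, the birth-outcome primary and the sample size of 782 are untouched.

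**What to change.** In Table 3 and section 8.1.3:

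- start counting and person-time for maternal malaria, parasitaemia and anaemia after the first study-drug dose, in line with the adverse-event window in section 7.1.2;
- classify enrolment and first-dose-visit samples as baseline, not outcome;
- pre-specify the enrolment haemoglobin or parasite status as a covariate in the corresponding GEE model;
- report the from-randomisation analysis alongside as a sensitivity analysis.

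The cost is a change of wording and a few lines of code; the dates and enrolment values are already collected. The downside is that women who leave before the first dose drop out of these three analyses. If the planned 5% loss is spread evenly over follow-up, that is 782 × 0.05 × 2.0/23.5, or about 3 women. Little bias is expected, because allocation is blinded and no drug has yet been given.
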